Beyond non-contact thermographic screening, deeper concerns for public health have arisen with a related non-contact technology. Specifically, the concern is with an existing FDA-approved class of non-contact single pixel (single pixel meaning non-thermographic, or non-image-based) infrared (IR) scanning systems configured to perform IR temperature measurements of the forehead and report an extrapolated core body temperature. FDA-approved devices within this class have been observed to report healthy body temperatures in conditions that should preclude an accurate measurement (e.g. being operated outdoors in inclement conditions), which has led to many clinicians being wary of trusting these devices. Furthermore these devices have also been observed to report temperatures all within a

normal range between 97 and 99F when operated on an IR calibration source having simulated body temperatures covering the range from 95F to 103F, which is a clear cause for concern. This specific observation has led to published reports documenting the use of “bias-to-normal” algorithms that take a range of input temperature measurements and output a smaller range of temperatures closer to the normal body temperature. This is difficult to detect due to the limited spread in normal core body temperatures in the healthy population, and in fact, by generating a made-up temperature from 98.6 plus or minus a small random fraction less than 1, one can produce an apparently-functional body temperature measurement system that is difficult to distinguish from the oral temperature measurement. Due to the presence of documented bias-to-normal algorithms, it is clear that improvements in test methods are desperately needed. Until such time, any evaluation must include a range of actual core body temperatures extending into diagnostically-relevant high temperatures (individuals having real fevers) or it will be difficult to detect a bias-to-normal algorithm.

[figure not shown]

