Several other non-contact thermographic and single-pixel NCIT systems are available for use in this study. These are referred to as the **secondary** non-contact systems and each measurement will be denoted by the system or manufacturer name. Each system will be set up following the manufacturer's operating instructions, similarly to the primary non-contact system and immediately adjacent to said primary system. Each secondary system will be configured in logging mode, if a mode that records the estimated core temperature with a timestamp is available. If such mode is not available on a particular system, said system will be associated with a clipboard for manually logging the system's output along with the unique number outputted by the primary system upon scanning the participant.

Controlled Temperature Rooms

Please refer to the image above, which is reproduced from page 3 of the Study Schema document. This study requires four rooms having independent control of air temperature to gradients above or below the primary setpoint of the building and a main area at the primary setpoint of the building. This main area may consist of two rooms (e.g. Room A and the room containing both Oral and IR thermometry stations above), one for acquiring IR thermometry and oral temperatures and a second for blinded ambient temperature or a single room

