The rooms will each consist of a portable tent with dimensions of at least 5x5ft base and height of 6ft. The critical requirement of said tent is sufficient thermal isolation from ambient temperatures to allow the maintenance of the required elevated or cooled temperature setpoints to within 1.8F. At present time, the most suitable tent is the THUNDERBAY Ice Cube 3 Man Portable Ice Shelter <https://www.amazon.com/gp/product/B019CU59VI>. This tent is surprisingly large, and has sufficient space to allow four adults to stand with 2 feet between adjacent people or two people with over 3 feet between them. The thermal radiant intensity of the walls of this tent do not match that of the elevated or cooled air temperature, because these walls directly contact and conduct to the ambient air and equilibrate between the ambient and internal temperatures, thus they radiate closer to the ambient temperature. Therefore, additional radiating membranes are used, consisting of sheets of fabric or paper hung from the ceiling or otherwise mounted with at least several inches displacement from the walls and having sufficient but low level of air flow to equilibrate the majority of the membrane to the internal air temperature. A GFCI-protected extension cord and powerstrip will be used to provide power to each tent.

The formula relied upon to obtain the ideal elevated temperatures is as follows, given as a lambda expression, which incorporates a first lambda (Python):

- $core2surf = \lambda core, air: core - (core-air)*0.191$

- $get_needed_room_air = \lambda air, febrile: core2surf(febrile, air) - ((98.6 - core2surf(febrile, air))/0.236)$

This gives us the needed heating temperature to get a desired change in body temperature, e.g. $get_needed_room_air(68, 100.4)$ returns 75.6F, meaning, in order to simulate a 100.4F core

temperature, a person must equilibrate to 75.6F air temperature before returning to receive a scan from the primary scanner located in 68F air temperature. This can be summarized more simply as, for every 1C (1.8F) elevation desired, the heated room must be that multiple of 4.23C (7.62F) above the scanning area's air temperature. Note, the exact coefficient was determined in a pilot study performed in June 2020, and may be refined by this study, which could alter the expected induced core temperatures.

Detailed Procedure - Blinded Temperature Study

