In a second analysis, the equilibration time constants will be evaluated for possible linear correlations with the demographic data, although it is possible the small sample size and variability will preclude the detection of any significant correlations. In case there are nonlinear relations, scatter plots will be examined to determine if a low-order polynomial or other reasonable fit could explain a relation, while keeping in mind the fact each additional test is a multiple comparison, thus increasing the required p-value multiplicatively. Scatter-plots, trends and r-values will be reported, and this data may be collated with future collections of independent datasets.

The controlled face temperature data will be analyzed for sensitivity and specificity of each non-contact system used, first in a blinded analysis and then in an open-label analysis. First, the blinded face temperature data will be used to assign each recorded datapoint into normal, mild and moderate and severe fever groups, corresponding to below 38C (100.4F), 38-39C (100.4-102.2F), 39-40C (102.2-104F) and above 40C (104F). Note, the heated rooms' air temperatures were selected to produce simulated core temperatures that straddle the mild and moderate thresholds (hence, a well-performing system should place 50% of the measurements above the threshold and 50% below while a system relying on a bias-to-normal method might place only 10% above the selected threshold), therefore the severe fevers group

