should likewise have few subjects placed within it. The sensitivity and specificity for assessing each of a mild and a moderate fever temperature will be assessed in a straightforward manner by revealing the labels and determining the fractions of correctly- and incorrectly-labelled datasets. These labels are generated by first matching the NFC UUID associated with an *nfc-temperature-scan* to the previous closest in time *nfc-room-scan* of this same NFC UUID and taking that room's air temperature difference to the temperature scanner's air temperature and converting to simulated core body temperature. Next, this now open-label data will be used to determine the mean and standard deviation across the core temperature scans of each of these four groups. The standard deviation of oral temperatures below the 38C threshold will be used to determine the false positive rate, using an assumed normal distribution or a low-dimensional parametric fit to the actual oral distribution. A parametric fit to the distribution above 38C will be used to determine the sensitivity and specificity for mild, moderate and severe fever thresholds, corresponding to 38-39C, 39-40C and 40C and above, respectively, using the sum of the area under the curve above the appropriate threshold. The linear correlation between oral and imaging temperatures in the below-threshold range will be tested for significance. A subset of the data consisting of equal parts of over-threshold (fevers, by oral temperatures) and under-threshold participants will be tested for significance, and this significance level compared with that of the whole set.

In a second analysis, the controlled face temperature data will be analyzed for effect of confounds with the primary non-contact thermographic system. In this case, the physiologic correction parameters obtained from each individual will be examined for linear correlates or nonlinear relationships with the demographic data. As with the equilibration data, scatter-plots, trends and r-values will be reported, and this data may be collated with future collections of independent datasets.

Quality control and data management

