Appendix - Physiologic Model

There is considerable published research on the heat transfer properties of human skin, with the original bioheat transfer equation (Pennes 1948) based on thermal conductivity of tissue, perfusion and blood density. Over the years, modifications were proposed incorporating fluid flow, viscosity and radiative effects (Wulff, Liu) primarily to better model dynamic effects. However, in static equilibrium the theoretical model is approximated sufficiently well by the Fourier heat equation. The model assumes that due to the anatomy of the angular artery, the tissue located a few mm beneath the skin of the inner canthus is at core body temperature. At the surface of the skin, the surface temperature is set by the heat flow through this thin layer of skin and then emitted to the ambient by radiative and convective routes to the air. The conduction through skin can be approximated to be proportional to the delta between core and surface skin temperature divided by a thermal resistance we do not need to know if we know the skin temperature and ambient temperature because the heat flow from core to skin is equal to the heat flow from skin to ambient air.

Radiative dissipation for typical body and ambient temperatures can be linearly approximated to good accuracy as 6 Watts per square meter times the delta in temperature between skin and ambient (C), and radiative dissipation is within an order of magnitude of the conductive plus convective pathway which is also proportional to the delta between skin and ambient temperatures. Because these are proportional to the delta, and if the air conditions are still and not excessively humid, the effect is linearly dependent on the delta and can be measured and used to perform a physiologic correction on the measured surface temperature in order to determine core body temperature to sufficiently good accuracy (0.5C). The primary sources of error in the physiologic correction are the air conditions, which can alter the

convective dissipation to ambient by a factor of two or more, and the thickness and other properties of the skin layer between core and inner canthus skin. Nevertheless, these have been observed by clinical study to be sufficiently consistent from person to person to serve as a modality for obtaining core body temperature. This model is used to perform a physiologic correction taking ambient air temperature to convert an inner canthus skin temperature to a core body temperature.

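### Fever labels built on an inner-canthus coefficient are used to score every non-contact system, so heated-room labels for forehead thermometers hold only if the forehead coefficient is also about 0.191

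*Combined protocol and SAP*

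**What the plan says.** Scope of scoring (section D, Analyses): "The controlled face temperature data will be analyzed for sensitivity and specificity of each non-contact system used, first in a blinded analysis". Section B, Secondary Non-Contact Equipment, says: "Several other non-contact thermographic and single-pixel NCIT systems are available for use in this study". The Introduction describes the single-pixel class as "scanning systems configured to perform IR temperature measurements of the forehead and report an extrapolated core body temperature".

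Label (section D): each scan is matched to the participant's last room. That room's air temperature is compared with the scanner's "air temperature and converting to simulated core body temperature". The rule does not vary by device or by measurement site.

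Conversion (section B, Controlled Temperature Rooms): surface temperature is "core - (core-air)*0.191", and the room-setting formula uses 0.236. The coefficient is said to come from a June 2020 pilot and may be refined in this study.

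Site of the model (Appendix - Physiologic Model): because of the angular artery, "the tissue located a few mm beneath the skin of the inner canthus is at core body temperature". The Appendix describes the model as turning inner canthus skin temperature into core temperature, and lists the skin layer over that site among the main sources of error. The equilibration phase, which supplies the data for refinement, measures the inner canthi.

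**The concern.** A true fever raises the temperature beneath every skin site. A heated room leaves core temperature alone and warms each site according to that site's own coupling to the air. The label therefore states what the room simulates at one site, the inner canthus. When it is used as the reference standard for a device reading another site, the device is compared with a core rise that its site may not have been given.

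The design is sensitive to this because the heated rooms are placed on the fever thresholds. Section D expects a good system to put 50% of readings above the threshold and suggests a biased one might put only 10% there. A modest mismatch can move an honest forehead device well away from 50%, or bring a device that compresses its output closer to 50%. Assessing device sensitivity and specificity is one of the study's two stated aims, and the Introduction singles out forehead devices as a worry.

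**Working it through.** **Inputs from the documents.** k = 0.191 and ratio 0.236; blinded rooms at 68, 75.6 and 83.2F with scanning at 68F (Controlled Temperature Rooms), so air differences of 0, 7.6 and 15.2F; SD 1.11F for surface data and at most 0.48F for the physiologic component (Population Size); thresholds 100.4F and 102.2F (section D). The baseline is 98.6F, as in the room formula.

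**Assumed.** Forehead coefficient kf from 0.15 to 0.35; full equilibration; normal readings; a device that corrects for ambient air with its own site's coefficient.

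**Reproducing the plan's figures.**
- For 100.4F: surface = 100.4 - 32.4 x 0.191 = 94.21; room = 94.21 - (98.6 - 94.21)/0.236 = 75.6F.
- For 102.2F: surface = 95.67; room = 83.2F.
- 0.191/0.809 = 0.236, and 1.8 x 0.809/0.191 = 7.62F per 1.8F. All agree with the protocol.

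**General form.** After equilibration to room air R, a site with coefficient k has surface temperature S = C - k(C - R). Scanned in air A and corrected with the same k, the estimate is (S - kA)/(1 - k) = C + [k/(1 - k)](R - A). The label equals this only where k = 0.191.

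**Simulated rise, and share of Room B readings above 100.4F for an honest device** (plan expects 50%):

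| kf | Room B rise | Room C rise | Share, SD 0.48F | Share, SD 1.11F |
|---|---|---|---|---|
| 0.15 | +1.3F | +2.7F | 17% | 34% |
| 0.17 | +1.6F | +3.1F | 31% | 41% |
| 0.191 | +1.8F | +3.6F | 50% | 50% |
| 0.25 | +2.5F | +5.1F | 94% | 75% |
| 0.30 | +3.3F | +6.5F | nearly 100% | 91% |
| 0.35 | +4.1F | +8.2F | 100% | 98% |

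Room A has an air difference of about zero, so its label is right for any kf.

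**False positives at 102.2F.** With kf = 0.30, Room B averages 98.6 + 3.26 = 101.86F. The share above 102.2F at SD 0.48F is the normal tail beyond (102.2 - 101.86)/0.48 = 0.71, about 24%.

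**Masking.** A device that multiplies every deviation from 98.6F by c matches the labels when c x kf/(1 - kf) = 0.236. That gives kf of about 0.24 for c = 0.75, 0.32 for c = 0.5 and 0.49 for c = 0.25. The Introduction's example (95 to 103F in, 97 to 99F out) is c = 2/8 = 0.25. At kf = 0.35 such a device shows 0.25 x 4.09 = +1.0F in Room B and 0.25 x 8.18 = +2.0F in Room C, against labels of +1.8F and +3.6F.

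**The case against.** **Size and direction.** The documents give no forehead coefficient, so they do not show whether forehead devices would be flattered or penalised. This stands; every forehead figure above is conditional on kf.

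**Ambient correction.** The shifts assume a device corrects for air temperature at its own site, and the Introduction doubts that most systems account for the environment at all. A fixed-offset device would show only kf times the air difference: at kf = 0.25, 0.25 x 7.6 = +1.9F and 0.25 x 15.2 = +3.8F, close to the labels. This also stands and limits the table to ambient-corrected devices. It does not rescue the label: agreement would then reflect two mismatches that happen to cancel.

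**Specificity.** A reader might infer that false positives rise throughout. They do not. Room A supplies most true normals and is unaffected. With kf above 0.191, Room C over-readings are still correct positives at 100.4F. The exposure is Room B scans labelled just under 100.4F, and Room B scans at 102.2F.

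**Bias-to-normal.** A reader might infer that the compression the Introduction describes would be hidden. Within the assumed range it would still show, and a device that simply outputs 98.6F plus noise ignores the room and cannot be masked by any kf.

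**Source of 0.191.** The Appendix supplies the linear form and the site; the value came from the pilot. The label's tie to the canthus therefore rests on the Appendix's account of the model, not on a derivation of 0.191 there.

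**Scope.** The blinded procedure sends participants to further thermographic equipment, and single-pixel systems are listed as available rather than committed. The evaluation supplement and performance-standard addendum are cited but not in the text reviewed, so handling there cannot be excluded. Even so, section D covers every system used and contains no site restriction.

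**Conclusion.** The point holds in a limited form. Section D gives forehead devices a reference standard that is valid in Rooms B and C only if kf is about 0.191. Nothing in the text claims or tests that, and the planned refinement measures the canthi.

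Over an assumed kf of 0.15 to 0.35, Room B simulates +1.3F to +4.1F instead of +1.8F, and Room C +2.7F to +8.2F instead of +3.6F. An honest, ambient-corrected device with SD 0.48F would place 31% (kf 0.17) or 94% (kf 0.25) above 100.4F in Room B. If kf is lower than 0.191, honest devices are charged missed fevers. If it is higher, mild to moderate compression can be masked and some Room B readings become false positives at 102.2F.

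The documents do not support reading this as a flaw in the whole sensitivity and specificity analysis. Results for inner-canthus systems, including the primary one, are untouched by it. It should be fixed, but it affects only secondary devices that read the forehead.

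**What to change.** 1. Record the measurement site of each secondary system, alongside the system or manufacturer name already planned.
2. In section D, limit the simulated-core labels, and the sensitivity and specificity built on them, to systems that read the inner canthus.
3. For forehead systems, report output by room and its change per degree of room-minus-scanner air difference, without fever sensitivity or specificity. A slope near zero would still expose a device that ignores its input.
4. Only if the forehead is visible in the stored Room D and E thermographs, estimate kf there and report site-specific labels, using kf/(1 - kf), as exploratory. The seating instructions require only that the eyes stay in view, so this may not be possible.

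Items 1 to 3 change only record-keeping and analysis wording, and nothing adds a participant procedure; item 4 adds a second image region to process. The downside is that forehead devices may end with no fever sensitivity or specificity figure.

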The number of samples required to understand the impact of environmental or physiological confounds on surface temperature is dependent on the variability in the core-to-surface temperature physiologic offset. The variability in core body temperature has been found to be close to 1F but note the research design proposed here is not dependent on normal person-to-person variability in core temperature because the temperatures obtained are all referenced to each individual's core temperature. To estimate the likely physiologic variability in the population, we can extrapolate based on surface temperature data taken by the primary thermographic system obtained over the past six months because this should be approximately the vector sum of variability in core temperature, measurement accuracy, and the physiologic variability. This data must be interpreted with caution, because these have been obtained with less control over environmental conditions and furthermore we do not know the core body temperature variability in the preliminary data population, but it can provide a reasonable error bound. This data shows a standard deviation of 1.11F (note, this value is obtained without *any* bias-to-normal algorithm, which appears to be a novel feature in this research), which would suggest the physiologic variability component is at most 0.48F, or half a degree. Therefore, in order to determine the sensitivity and specificity at detecting elevated temperatures of 1.8F (100.4F threshold) to within 20% (meaning, can we significantly distinguish 100.40 from 100.04F with the aforementioned standard deviation in a one-sided paired t-test), we require 28 participants. To account for possible data collection failures, we intend to recruit as many as 45 participants.

Data Collection

- Demographic and clinical data: minimal demographic and clinical data will be collected by interview with the participant at the time of the imaging studies including age, gender, any disease- or autonomic-modulating treatment, height, weight and any antipyretic medications in past 12 hours in order to allow adjustment for confounding factors. We do not intend to collect data on menstrual cycle due to the additional potential privacy concerns this will place on participants worried about this data which is significantly more sensitive than other data being collected.

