Each participant is given a random room letter provided by a display configured to output a letter randomly pulled from a uniform distribution of the room numbers A, B and C. The participant is to go to said room and locate the NFC scanner inside and scan their data collection form to obtain their **nfc-room-scan** (to be used in later identifying which temperature group their body is simulating). Once the participant has entered a room, the door to the room is closed and the participant is instructed to wait while remaining relatively still for ten minutes while avoiding touching their faces and avoiding stressful content (e.g. avoid browsing the internet). At the conclusion of the ten minutes, determined by study personnel, the door will be opened and the subjects will exit the room and walk to the scanning area to scan their data collection form to obtain their **nfc-temperature-scan** and receive three consecutive face scans. After these scans are complete, participants will proceed to additional thermographic face scanning equipment to receive additional scans within one minute of exiting the equilibration room. Study personnel will record the results of any additional equipment scans along with a unique number displayed on the primary thermographic system display at the conclusion of their primary temperature scan. Study personnel will then obtain an oral thermometry measurement. After all oral and IR thermometry measurements are complete, participants will proceed to the next blinded temperature room and the above process is repeated. This is repeated until all participants have received scans after spending ten minutes in all three blinded temperature rooms, at which point they proceed to one of the equilibration rooms, described below.

Detailed Procedure - Equilibration Study

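### The oral-imaging correlation tests define no analysis unit and account for neither participant nor room, so their error rate can be well above or well below 5%

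*Combined protocol and SAP*

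**What the plan says.** Under Detailed Procedure - Blinded Temperature Study, participants leave each of the three rooms and "receive three consecutive face scans". Oral Thermometry adds one oral reading after each set of non-contact measurements. That makes nine primary-system scans and three oral readings per person in this phase.

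Section D. Analyses says the face temperature data "will be used to assign each recorded datapoint into normal, mild and moderate and severe fever groups". It obtains sensitivity and specificity by "determining the fractions of correctly- and incorrectly-labelled datasets", and summarises each fever group by a mean and SD across scans. It continues: "The linear correlation between oral and imaging temperatures in the below-threshold range will be tested for significance". A second test uses a subset with equal parts over and under threshold, described by participants, and its significance level is compared with that of the whole set.

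The terms datapoint and dataset are not defined. The unit for the correlation tests is not given. Nothing averages the three scans, fits a participant effect or adjusts for room. Population Size counts people: "we require 28 participants", and "we intend to recruit as many as 45 participants".

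**The concern.** Three scans taken within about 10 seconds share one face and one oral value, and the three visits share one person. A standard correlation test assumes independent pairs. Counting scans or visits as independent lowers the bar for significance.

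The rooms act in the other direction. They are designed to move imaging by several times the person-to-person SD, while no matching change in oral temperature is planned. If rooms are pooled without a room term, that designed variation is treated as noise and hides the relation between people.

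The p-value is itself an output here, because two significance levels are to be compared. With an undefined unit and room mix, a difference between them may reflect only how many readings were counted and from which rooms.

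**Working it through.** **The plan's own figure.** Population Size says: "This data shows a standard deviation of 1.11F". Removing a core SD of 1F gives √(1.11² − 1²) = 0.482F, which matches the statement that "the physiologic variability component is at most 0.48F". The difference to detect is 100.40 − 100.04 = 0.36F. A one-sided 5% paired t criterion with SD 1.11F and no power term gives √28 × 0.36/1.11 = 1.716, just above t(0.95, 27) = 1.703, so n = 28. Alpha and power are not stated and other inputs also give 28, so this match is not unique. In any case the study is sized in participants.

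**Counts.** 28 × 3 = 84 visits and oral readings; 84 × 3 = 252 scans (135 and 405 at 45 participants). The two-sided 5% critical |r| is 0.374 at n = 28, 0.215 at 84 and 0.124 at 252.

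**Room shift.** Controlled Temperature Rooms gives targets of 68, 75.6 and 83.2F, and 1.8F of simulated core temperature per 7.62F of air. So 7.6/7.62 × 1.8 ≈ 1.8F and 15.2/7.62 × 1.8 ≈ 3.6F. Shifts of 0, 1.8 and 3.6F have variance (1.8² + 0 + 1.8²)/3 = 2.16F².

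**Variances for a device unrelated to oral temperature.** From the documents: person offset SD 0.48F (0.2304) and oral SD 1F between people (1.00). Assumed: visit noise 0.2F on both measures (0.04) and scan noise 0.18F (0.0324). Without room shift, imaging variance per scan is 0.2304 + 0.04 + 0.0324 = 0.3028. Oral variance is 1.04.

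**Formula.** With k values per visit, the variance of the sample correlation under no association is inflated by about

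V = 1 + (k − 1)·a·b + 2k·c·d

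Here a and b are the oral and imaging correlations within a visit (a = 1, since one oral value is repeated), and c and d are those between visits (c = 1/1.04 = 0.962). The last term drops out for a single room. The false-positive rate is 2[1 − Φ(1.96/√V)].

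- Room A, scans: b = 0.2704/0.3028 = 0.893; V = 1 + 2 × 0.893 = 2.79; rate 24%.
- All rooms, scans, no shift: d = 0.2304/0.3028 = 0.761; V = 1 + 1.786 + 6 × 0.962 × 0.761 = 7.18; rate 46%.
- All rooms, scans, full shift: imaging variance 0.3028 + 2.16 = 2.4628. The mean shift covariance between different rooms is −6.48/6 = −1.08, so d = (0.2304 − 1.08)/2.4628 = −0.345. b = 2.4304/2.4628 = 0.987. V = 1 + 1.974 − 1.990 = 0.98; rate 4.8%.
- All rooms, visit means, no shift: variance 0.2304 + 0.04 + 0.0324/3 = 0.2812; d = 0.819; V = 1 + 2 × 0.962 × 0.819 = 2.58; rate 22%.
- All rooms, visit means, full shift: d = −0.8496/2.4412 = −0.348; V = 1 − 0.669 = 0.33; rate 0.1%.

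**Simulation (4,000 studies per setting, 28 people)** agrees:

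| Data tested | Rate at nominal 5% |
|---|---|
| Room A, scans | about 25% |
| Room A, one mean per person | about 5% |
| All rooms, scans, no room shift | about 47% |
| All rooms, visit means, no room shift | about 23% |
| All rooms, scans, full shift | about 5% |
| All rooms, visit means, full shift | about 0.1% |
| Scans labelled below 38C, full shift, label SD 0.6F assumed | about 15% (17% in a repeat run) |
| One mean per participant over all rooms | about 5% |

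**Which set is below threshold?** The plan does not say whether oral, imaging or labelled temperature decides. If oral does, the cut at 100.4F is 1.8 SD above 98.6F. About 96% of readings then qualify, and this test is close to the pooled one.

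**The case against.** A reader might infer that the plan makes each scan an independent unit and so treats 28 people as 252. The text does not say that. Datapoint is undefined, its sentence concerns sorting into fever groups, the room label attaches to a visit, and the balanced subset is described by participants. The scan is one reading and 252 is its upper bound at 28 people.

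A reader might also infer that a worthless device would pass the pooled test nearly half the time. The 47% needs a device that keeps a personal offset yet shows no room shift. With the designed shift, the pooled scan rate is about 5%. It is about 3% if below-threshold is decided by the imaging reading, with Room A centred 1.8F below the cut. A device that emits random values near 98.6F has no personal offset, so personal clustering does not arise.

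Nor are the accuracy results too precise as planned. No interval is specified for sensitivity or specificity, and clustering does not invalidate the point fractions. The confounder correlations use parameters obtained from each individual and are unaffected. Sensitivity and specificity are the main aim, the correlation tests are subsidiary, and the Introduction itself warns that linear correlation can mislead.

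All of this stands and limits the point. It does not show that the tests are sound. A pooled scan rate near 5% arises because two errors of opposite sign happen to cancel, and by visit the same data give almost no rejections. The equilibration analysis likewise names a two-sample t-test for heating against cooling although the same participants pass through both rooms. The silence on repeated measures is therefore more than terse drafting of one sentence.

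**Conclusion.** The point holds for the oral-imaging correlation tests. They are run on repeated readings from rooms with designed shifts, with no stated unit and no participant or room term. The p-value can err in either direction: too small in a single room or a label-defined low range analysed by scan (about 25% and 15% false positives), and far too conservative when rooms are pooled by visit with the full shift (near 0%). The planned comparison of subset and whole-set significance cannot be interpreted as written.

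The person offset and oral SDs come from the documents; visit noise, scan noise and label spread are assumptions. With all noise terms at 0.1F or 0.3F, the pooled scan rate is 51% or 43% without the shift, and 4.1% or 6.9% with it. Under a different parameterisation without room shift, person-level correlations of 0.3 to 0.9 in both measures give 23% to 50% by scan and 7% to 25% by visit. The planned accuracy fractions stand; only an interval added later at scan level would be too narrow.

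**What to change.** In D. Analyses:

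1. Define datapoint, dataset and below-threshold, and say which measurement decides the threshold.
2. Reduce the three consecutive scans to one value per visit (mean or median).
3. Test the oral-imaging relation in a model with a room term, or the actual difference in air temperature between room and scanner, and a participant random intercept. Alternatively, use one value per participant within a single room. A participant effect alone is not enough, because the room shift would still be treated as noise.
4. Use the same unit and model for the balanced subset and the whole set.
5. If intervals are reported for sensitivity or specificity, bootstrap by participant.

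The cost is analysis wording; all the data are already to be collected. Compared with scan-level tests, p-values in single-room or below-threshold sets will rise, and any intervals will widen.
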